3.2. Secondary Endpoint(s)

- *Other EORTC-QLQ-C30 subscales*
- *Other physical activity metrics (Steps, MVPA time)*
 - The main variables collected and/or derived from wearable device are shown in Table 2.
- *Adverse events and any laboratory abnormalities (Type, incidence, severity, seriousness and relationship to study medications)*

- *PRO-CTCAE (Fatigue and General pain)*
 - *The PRO-CTCAE is a PRO measurement system that includes a library of questions that measure symptomatic adverse events from the patient perspective. Seventy-eight symptom terms that are common in oncology clinical trials can be evaluable with PRO-CTCAE, and each of symptom terms is assessed relative to one or more distinct attributes, including frequency, severity, and/or interference with usual or daily activities. Responses are provided on a five-point Likert scale.*
- *Disease progression*
- *Patient treatment satisfaction*
 - *Treatment satisfaction will be evaluated with single item question (eg, “How satisfied are you with your current breast cancer treatment?”). Responses are provided on a five-point Likert scale.*
- *Palbociclib treatment (including dose, dose reduction, dose interruption, cycle delay)*

Table 2. Physical activity metrics variables from wearable device

Variables	Definition
Steps	Total estimated steps taken per Date.
Wear minutes	Total minutes of algorithmically detected “wear time”
Sedentary behavior	Number of total minutes defined as Sedentary Behavior as defined using the Staudenmayer '15 technique.
Light activity	Number of total minutes spent in Light activity category as defined using the Staudenmayer '15 technique.
Moderate activity	Number of total minutes spent in Moderate activity category as defined using the Staudenmayer '15 technique.
Vigorous activity	Number of total minutes spent in Vigorous activity category as defined using the Staudenmayer '15 technique.
MVPA	Total estimated number of minutes of Moderate or higher (moderate to vigorous) physical activity per Date as calculated using the Staudenmayer '15 technique.
Calories	Total estimated calories per Date as calculated using the “Hildebrand Nonlinear” technique.
MET	Total estimated METs per Date as calculated using the “Hildebrand Nonlinear” technique.

Note: All the physical activity metrics variables will be analyzed with “WAKEWEARFILTERED” (ie. “Wear” = TRUE. Excludes minutes that fall within a sleep period.)

CCI

[REDACTED]

[REDACTED]

[REDACTED]

[REDACTED]

3.4. Baseline Variables

Variables	Data Source	Description
Birth Year	eCRF	
Sex	eCRF	1: Male, 2: Female
Ethnicity	eCRF	
Race of Subject	eCRF	
Height	eCRF	Unit: cm
Weight	eCRF	Unit: kg
BMI	eCRF	Automatically calculated by the following formula BMI = weight (kg)/Height (m) ²
Medical History Term	eCRF	MedDRA terms including Lowest Level Term, Preferred Term, High Level Term, High Level Group Term, Primary System Organ Class) will be provided by auto-encoding
Name of Medication (Prior Drug Treatment for Breast Cancer)	eCRF	Standardized Medication Name based on WHO-DRUG will be provided by auto-encoding.
Reason for Stopping Therapy (Prior Drug Treatment for Breast Cancer)	eCRF	
Treatment (Prior Surgery for Breast Cancer)	eCRF	MedDRA terms including Lowest Level Term, Preferred Term, High Level Term, High Level Group Term, Primary System Organ Class) will be provided by auto-encoding
Date of initial diagnosis (Primary Diagnosis)	eCRF	
Date Recurrence/Metastatic (Primary Diagnosis)	eCRF	

Variables	Data Source	Description
TNM Stage Initial Diagnosis (Primary Diagnosis)	eCRF	
Metastatic Site (Primary Diagnosis)	eCRF	
Menopausal status	eCRF	
ECOG Performance Status	eCRF	
Line or therapy	eCRF	
Education	ePRO	
Employment	ePRO	
Physical activity	ActiGraph	Metrics for analysis are undergoing consideration.

4. ANALYSIS SETS (POPULATIONS FOR ANALYSIS)

Data for all participants will be assessed to determine if participants meet the criteria for inclusion in each analysis population prior to releasing the database and classifications will be documented per standard operating procedures.

Population	Description
Enrolled	All participants who sign the informed consent document.
Evaluable	All participants who enrolled in the study and who respond at least 1 item or measured at least 1 metrics of study application or device. Participants will be analyzed according to the enrolled group.
Safety	All participants who receive at least 1 dose of palbociclib or endocrine therapy. Participants will be analyzed according to the enrolled group. An enrolled but not treated participant will be excluded from the safety analyses.

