Patients will complete PRO assessment in weekly, and cycle-basis and wear the wearable device for 6 cycles. At the patients' regular clinical visits at approximately 30 day interval, they will bring the device worn in the past period, and study site staff will confirm if the returned wearable device is still functional and upload the physical activity data through Actigraph application (ie, ActiSync) into the Actigraph cloud system (ie, Actigraph CentrePoint). Detailed information will be included in User Manual and training for Actigraph CentrePoint for the sites. For the PRO and physical activity data collected from the patient, the data entry status or wearing status will be confirmed, but the data itself will not be confirmed. In addition, investigators or study site staff will complete eCRF to capture treatment changes and clinical outcomes (eg, adverse event) for 6 cycles after enrollment listed in SCHEDULE OF ACTIVITIES.

If a patient has not entered any data through ePRO application for 4 consecutive weeks or if a patient has not worn the wearable device for 4 consecutive weeks, the study site staff will be notified and asked to reach out to the patient.

Even if patients discontinue the initiated treatment before completion of 6 cycles and switch to another treatment, to assess association between change in QoL and physical activity versus disease progression, data collection (including PROs [EORTC-QLQ-C30 and PRO-CTCAE] and physical activity evaluation, EDC data entry) will continue to the end of the study (ie, 24 weeks after initiation of initial treatment).

End of Study

End of study is defined as end of 6 cycles of initiated treatment. If patients discontinue the initiated treatment before completion of 6 cycles (eg, due to disease progression) and switch to another treatment, end of study will be end of 24 weeks after initiation of initial treatment.

Investigators or study site staff will complete CRF to capture End of Study information listed in Section 6 SCHEDULE OF ACTIVITIES.

Patients will return the wearable device to study site staff. Study site staff will stop the collection of the physical activity data via configuration in Actigraph system (ie, Actigraph CentrePoint). Detailed information will be included in User Manual and training for Actigraph CentrePoint for the sites.

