16.2.4.2. Recording Non-serious AEs and SAEs on the CRF

During the active collection period, both non-serious AEs and SAEs are recorded on the CRF.

Follow-up by the investigator may be required until the event or its sequelae resolve or stabilize at a level acceptable to the investigator, and Pfizer concurs with that assessment.

If a patient begins a new anticancer therapy, the recording period for non-serious AEs ends at the time the new treatment is started; however, SAEs and research-related injury due to wearable device must continue to be recorded on the CRF during the above-indicated active collection period.

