2.2. Study Design

The study is a prospective, multicenter, observational study to evaluate PRO (Health related QOL) and physical activity using smartphone-based application and wearable device in Japanese patients with HR+/HER2- ABC.

Patients will be enrolled into either palbociclib plus endocrine therapy group (Group 1) or endocrine monotherapy group (Group 2) based on the discretion of the treating physician under routine clinical practice. Total target number of patients is approximately one-hundred in this study (About 50 patients in each group).

[figure not shown]
Enrolled patients will download a smartphone-based application for electronic PRO (ePRO), be provided access to and trained on the use of the application to complete baseline, daily, weekly, and cycle-based assessments for 6 cycles (24 weeks). In addition, enrolled patients will be provided with wearable device and requested to wear the device at all-times, except of while bathing and sleeping, for 6 cycles (24 weeks).

In this study, one cycle is defined as follows;

- In Group 1 (palbociclib plus endocrine therapy), palbociclib is administered for 3 consecutive weeks followed by 1 week off treatment to comprise one cycle of 4 weeks. If palbociclib is temporarily interrupted (eg, due to adverse event) and the start of the next cycle is delayed, the duration of one cycle may exceed 4 weeks, then, the observation period may exceed 24 weeks.
- In Group 2 (endocrine monotherapy), one cycle is defined as 4 weeks.

Participation in this study is not intended to change the routine treatment that patients receive as determined by their prescribing clinicians; all treatment decisions and type and timing of disease monitoring are at the discretion of the treating physician. No additional visits to the clinic will be required for the purposes of the study.

Figure 1. Study Design

It is anticipated that all data collection for this study will occur over a 18-month period (from the first patient's first visit to the last patient's end of study assessment),

Planned patient enrollment duration: 12 months

Planned data collection for an individual patient: 6 cycles (24 weeks*)

*In Group 1, if palbociclib is temporarily interrupted (eg, due to adverse event) and the start of the next cycle is delayed, the duration of one cycle may exceed 4 weeks, then, the observation period may exceed 24 weeks.

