6.5.2. Study Conduct and Participant Disposition

An accounting of the study patients will be tabulated including enrolled, evaluable for PRO, and safety (treated). Patients not meeting the eligibility criteria will be identified. Patients not completing the study will be listed along with the reason for their premature discontinuation.

Reasons for premature discontinuation will be summarized. Unexpected treatment (e.g., palbociclib therapy in Group 2) will be described.

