6.6. Safety Summaries and Analyses

Overall safety profile as characterized by type, frequency, severity of adverse events as graded by NCI Common Toxicity Criteria for Adverse Events version 4 (NCI CTCAE v.4.0), timing and relationship to treatment.

Adverse events will be classified using the MedDRA classification system. The severity of the toxicities will be graded according to the NCI CTCAE version 4. For other AEs without specific CTCAE definitions, results are identified according to CTCAE “other” categories.

Adverse events leading to death or discontinuation of study treatment, events classified as NCI CTCAE v.4.0 Grade 3 or higher, treatment-related events, study procedure-related events and serious adverse events will be considered with special attention.

Patients who start treatment are assessed for toxicities up to 28 days after the final dose of treatment or start of new treatment (whichever comes first). Toxicities observed beyond 28 days and recorded in the database per Sponsor’s agreement will be included in the summaries.

Frequency distributions of the worst grade of the adverse events will be summarized for all-causality and treatment-related adverse events, respectively. Grade 3 or higher events, serious adverse events, discontinuations due to adverse events will be summarized separately for all-causality and treatment-related adverse events. All adverse events including deaths and serious adverse events will be listed.

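### Safety is tabulated by enrolled group in a non-randomised study, which misplaces adverse events in a few definable cases that the toxicity window does not cover

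*SAP*

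**What the plan says.** SAP 4 (Analysis sets) defines the Safety population as "All participants who receive at least 1 dose of palbociclib or endocrine therapy. Participants will be analyzed according to the enrolled group". Enrolled patients who were never treated are left out.

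SAP 6.5.2 anticipates that treatment may not match the group: "Unexpected treatment (e.g., palbociclib therapy in Group 2) will be described". It gives no regrouping rule, and neither document plans a table by treatment received.

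Groups are formed "based on the discretion of the treating physician under routine clinical practice" (SAP 2.2; Protocol 9.1 says the same). Nothing is randomised.

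Two provisions limit which events are counted:

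- SAP 6.6 sets the window for treated patients, who "are assessed for toxicities up to 28 days after the final dose of treatment or start of new treatment (whichever comes first". An exception follows: "Toxicities observed beyond 28 days and recorded in the database" are included in the summaries if the sponsor agrees. No criterion for agreement is given.
- Protocol 16.2.4.2: once a patient begins a new anticancer therapy, "the recording period for non-serious AEs ends at the time the new treatment is started", whereas "SAEs and research-related injury due to wearable device must continue to be recorded on the CRF".

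Protocol 10 expects treatment changes within the 24 weeks and keeps collecting data "Even if patients discontinue the initiated treatment before completion of 6 cycles and switch to another treatment".

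**The concern.** Grouping by original assignment is worth having when it preserves a randomised comparison. Here the group is only a label for the regimen the physician intended to start. If a patient's treatment differs from that label, the enrolled-group rule puts her events under a regimen she did not receive. A description in the disposition section does not move those events.

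Adverse events, including their incidence and severity, are a secondary endpoint (Protocol 8.2, SAP 3.2), and analyses are summarised by group (Protocol 12.5). Readers will take the Group 2 column as the toxicity of endocrine monotherapy. That column may be small: Protocol 9.1 allows about 20 patients in a group, and the rationale for Amendment 2 in Protocol 4 records difficulty accruing Group 2. In so small a column, one misplaced patient is visible for events strongly linked to palbociclib.

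**Working it through.** The documents give no figure on this point, so there is nothing to reproduce. The check has two parts: which events the rule can misplace, and how much one misplaced patient matters.

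**Part 1. Which events reach the wrong column**

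| Situation | Provision that applies | Result under SAP 4 |
|---|---|---|
| Group 2 patient stops monotherapy, then starts palbociclib | SAP 6.6 closes the window at new treatment; Protocol 16.2.4.2 stops non-serious recording | Little palbociclib toxicity enters Group 2 |
| Group 2 patient takes palbociclib from the first dose | No cut-off applies | All her events count under monotherapy |
| Group 1 patient never takes palbociclib | No cut-off applies | All her events count under the combination |
| Palbociclib added to ongoing endocrine therapy in Group 2 | Depends on whether this is new treatment, which SAP 6.6 does not define | If not, later events count under monotherapy |
| Later events, mainly serious ones still recorded after a switch | Sponsor-agreement exception in SAP 6.6 | May enter the enrolled column |

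The fourth row is a real ambiguity. Protocol 16.2 uses one term, drug under study, for the advanced breast cancer treatment given within the observation period, and names both regimens under it. On that wording, added palbociclib could be read as drug under study and not as something new.

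**Part 2. Weight of one misplaced patient**

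Inputs:

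- Neutropenia, all grades: 81.8% with palbociclib plus letrozole, 6.3% with placebo plus letrozole (first-line trial summarised in SAP 2 and Protocol 7).
- Neutropenia in the fulvestrant trial, same sections: 84.1% vs 3.5%.
- Fatigue in the letrozole trial: 39.6% vs 28.4%.
- Group 2 size n: 20 and 80 are the ends of the range in Protocol 9.1; SAP 2.2 says about 50.
- Number of palbociclib-exposed patients in the Group 2 column, k: **not in the documents**. It is assumed, and all their events are assumed to be counted.

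Formula: expected Group 2 rate = [(n − k) × p_mono + k × p_palbo] / n. Each such patient therefore adds (p_palbo − p_mono) / n.

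Neutropenia, letrozole-trial rates, added per patient:

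- n = 20: (81.8 − 6.3)/20 = 75.5/20 = 3.8 points
- n = 50: 75.5/50 = 1.5 points
- n = 80: 75.5/80 = 0.9 points

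Expected Group 2 neutropenia, starting from 6.3%:

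| k (assumed) | n = 20 | n = 50 | n = 80 |
|---|---|---|---|
| 1 | 10.1% | 7.8% | 7.2% |
| 2 | 13.8% | 9.3% | 8.2% |
| 5 | 25.2% | 13.8% | 11.0% |

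Example for n = 20, k = 1: (19 × 6.3 + 81.8)/20 = 201.5/20 = 10.1%.

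With the fulvestrant-trial rates, each patient adds (84.1 − 3.5)/20 = 4.0 points at n = 20, taking 3.5% to 7.5%.

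Fatigue, n = 20, k = 1: (19 × 28.4 + 39.6)/20 = 579.2/20 = 29.0%, from 28.4%, a shift of 0.6 points.

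If the column held only patients who received monotherapy, the expected neutropenia rate would be 6.3% (or 3.5%) whatever the value of k.

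**The case against.** The strongest reply is that the plan already handles most of this. A reader might infer from SAP 4 and SAP 6.5.2 that palbociclib toxicity will generally flow into the monotherapy column. The documents do not support that: for the ordinary switcher, SAP 6.6 and Protocol 16.2.4.2 together remove most of it. This part of the reply stands.

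The second reply is that mismatches should be rare. Inclusion criterion 4 (Protocol 9.1.1) requires the patient to be starting one of the two regimens at entry, so enrolled group and first treatment should nearly coincide, and SAP 6.5.2 itself calls the deviation unexpected. This also stands, and it bears on how often the problem arises. It does not give a reason for preferring enrolled group when the two differ.

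Third, a reader might take 10.1% or 13.8% as a forecast. It is not one. Those figures combine the smallest planned group, an event with a very large contrast between regimens and an assumed number of patients. At n = 20 a single patient carries 1/20 = 5 points in any case.

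Fourth, the study is descriptive, SAP 5.1 rules out test-based decisions on safety, and all events are listed, so a careful reader could trace such a patient. No inference is therefore at risk. But in a descriptive study the labelled rate is the result, and a listing does not correct a table.

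**Conclusion.** The point holds in a limited form. Grouping safety by enrolled group gains nothing without randomisation. It misplaces events in three situations: a first treatment that differs from the enrolled group, in either direction; palbociclib added to ongoing monotherapy and not counted as new treatment; and later events admitted by sponsor agreement. For patients who simply switch, the existing cut-offs already contain the problem for most non-serious toxicity.

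The size is about 3.8 points of expected Group 2 neutropenia per affected patient at n = 20, 1.5 at n = 50 and 0.9 at n = 80, using the first-line letrozole rates and assuming that all of her events are counted. Fatigue hardly changes. The number of affected patients is unknown and probably small. This is a labelling error in a descriptive table that is cheap to prevent; it does not threaten the primary results.

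**What to change.** 1. **SAP 4.** Tabulate the Safety set by the treatment actually received at the start of the initiated treatment. Apply this in both directions: a Group 2 patient who starts on palbociclib goes under the combination, and a Group 1 patient who never takes it goes under monotherapy. Footnote the number reassigned each way.
2. **SAP 6.6.** Define new treatment. State that, for the adverse event tables, palbociclib added to ongoing monotherapy counts as the start of new treatment. Events before that date stay under monotherapy; recorded events after it go in a separate table. The same separate table can take post-switch events admitted by sponsor agreement.

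A rule that moved every patient with any palbociclib exposure to the combination column would not do: it would carry events that occurred on monotherapy into that column, and it would leave new treatment undefined.

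The separate table needs a caution. Sites that regarded added palbociclib as a new anticancer therapy may have stopped recording non-serious events under Protocol 16.2.4.2, so its non-serious counts may be incomplete.

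Cost: a few sentences in the SAP, a small amount of extra programming, and safety group counts that may differ slightly from the enrolled counts. Treatment type and duration are collected in both groups (Protocol 6, note f), so classification needs no new data.

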10. STUDY PROCEDURES

Screening and Baseline period

Study investigators will screen patients for eligibility, obtain informed consent, and enroll patients meeting the eligibility criteria. Informed consent must be obtained before any study specific procedures are performed. Patient eligibility will be reviewed and confirmed by investigator or study site staff before patients are enrolled in the study.

Investigators or study site staff will complete eCRFs to capture demographic, medical history, and treatment information at screening listed in Section 6 SCHEDULE OF ACTIVITIES.

Enrolled patients will download a smartphone-based application for ePRO into their own device (ie, Bring Your Own Device [BYOD]), be provided access to and trained on the use of the application to complete baseline, weekly, and cycle-based assessments for 6 cycles. As for data to be evaluated, see “PRO data via smartphone-based application” in Section 6 “Schedule of Activities”. Patients will complete baseline assessment for EORTC-QLQ-C30 and PRO-CTCAE at study site, if possible.

Investigators or study site staff will assign the wearable device to patients, and patients will be provided with the assigned device and be requested to wear the device at all-times, except of while bathing and sleeping, for 6 cycles. As baseline observation period, it is recommended to wear the device soon after obtaining informed consent until initiating the study treatment. At least 4 days is recommended for baseline observation period to obtain stable baseline data, but treatment schedule of each patient should be prioritized.

Observation Period

PFIZER CONFIDENTIAL

The observation period in this study will be 6 cycles (24 weeks).

In Group 1, palbociclib is administered for 3 consecutive weeks followed by 1 week off treatment to comprise 1 cycle of 4 weeks. If palbociclib is temporarily interrupted (eg, due to adverse event) and the start of the next cycle is delayed, the duration of 1 cycle may exceed 4 weeks, then, the observation period may exceed 24 weeks. In Group 2, one cycle is defined as 4 weeks.

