16. MANAGEMENT AND REPORTING OF ADVERSE EVENTS/ADVERSE REACTIONS REQUIREMENTS

This study includes qualifying diagnostic or monitoring procedures required per protocol to collect clinical data needed to meet the study objectives, which are not standard-of-care but that do not pose more than a minimal risk or burden to the study subject. The qualifying procedure in this study is physical activity data collection using wearable device.

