16.1. Adverse Events (AE)

An AE is defined as any untoward medical occurrence and can therefore be any unfavorable and unintended sign (including an abnormal laboratory finding), symptom, or disease, whether or not related to the subject's participation in the study.

AE reporting period for each subject begins from the time the subject provides informed consent, through the end of the observation period of the study which must include at least 28 calendar days following the last administration of the drug under study. **Any AE related to**

PFIZER CONFIDENTIAL

above procedure that occurs from the time the subject consents to the clinical research through and including 12 hours after completion of the qualifying procedure must be recorded. The investigator is required to assess whether the AE may be related to the subject's participation in the study. All AEs (ie, serious and non-serious, including those attributed to qualifying procedure identified as research-related injury) are collected in the clinical study database.

The investigator must pursue and obtain information adequate to determine the outcome of the AE and to assess whether it meets the criteria for classification as a research-related injury requiring immediate notification to Pfizer as described below.

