16.2.5. Causality Assessment

The investigator's assessment of causality must be provided for all AEs (serious and non-serious); the investigator must record the causal relationship on the CRF, and report such an assessment in accordance with the SAE reporting requirements, if applicable. An investigator's causality assessment is the determination of whether there exists a reasonable possibility that the drug under study caused or contributed to an AE; generally the facts (evidence) or arguments to suggest a causal relationship should be provided. If the investigator does not know whether or not the drug under study caused the event, then the

PFIZER CONFIDENTIAL

event will be handled as “related to drug under study” for reporting purposes, as defined by the sponsor. If the investigator's causality assessment is “unknown but not related” to drug under study, this should be clearly documented on study records.

In addition, if the investigator determines that an SAE is associated with study procedures, the investigator must record this causal relationship in the source documents and CRF, and report such an assessment in the dedicated section of the CT SAE Report Form and in accordance with the SAE reporting requirements.

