18.2. Compensation

If an adverse event occurs during the study, the investigator will promptly take necessary measures (investigation, treatment, and study discontinuation) to ensure the safety of the study participants. In such case, the best medical care within the range of public health insurance treatment shall be provided. Compensation will be made for injury associated with the procedures required for participation in this study (ie, wearing of wearable device). However, compensation will not be made for other injury. Investigator shall take necessary measures such as insurance for indemnification before the start of this study in preparation for liability.

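### The SAP's safety set and cut-off follow drug exposure, so some wearable-related events and post-switch SAEs that the protocol collects are excluded from, or not assured a place in, the safety summaries.

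*SAP*

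**What the plan says.** **Protocol.** Section 16 identifies what the study adds to routine care: "The qualifying procedure in this study is physical activity data collection using wearable device". Section 18.2 limits compensation in the same way: "Compensation will be made for injury associated with the procedures required for participation in this study (ie, wearing of wearable device").

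The device has its own collection period. Under Section 16.1, any adverse event related to it, from consent "through and including 12 hours after completion of the qualifying procedure must be recorded". Wear begins before treatment; in Section 10, "it is recommended to wear the device soon after obtaining informed consent until initiating the study treatment". It also continues after a change of treatment, because Sections 6 and 10 keep physical activity collection running to 24 weeks after the initial treatment began.

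Section 16.2.4.2 closes the recording of non-serious events when a new anticancer therapy starts, with an express exception: "SAEs and research-related injury due to wearable device must continue to be recorded on the CRF" for the rest of the active collection period.

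**SAP.** Section 4 requires at least one dose of palbociclib or endocrine therapy for the Safety set, and states: "An enrolled but not treated participant will be excluded from the safety analyses". Section 6.6 says that, once dosed, a participant is "assessed for toxicities up to 28 days after the final dose of treatment or start of new treatment (whichever comes first"). It promises special attention to procedure-related events, a listing of all adverse events, and inclusion of toxicities beyond 28 days if they are in the database by sponsor agreement. The summaries it specifies are all-causality and treatment-related only.

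**The concern.** The protocol runs two clocks: one for the drugs, and one for the wearable that starts at consent and does not stop at a therapy switch. The SAP runs only the drug clock. Events that sites must record on the device clock can therefore sit in the database and be left out of the safety tables by the SAP's stated rules.

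At stake is whether the final report can summarise device-related events over the period in which the device was worn. The same cut-off also touches SAEs of any cause after a switch. Protocol 16.2.4.1 and 16.2.4.2 require these to be reported and recorded despite the new therapy, yet the SAP's window has closed by then.

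**Working it through.** The plan states no figure on this point. The check sets the collection rules beside the analysis rules for each type of event, then illustrates how much wear time could be involved.

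**1. Event by event**

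| Event | Collected under the protocol? | Treatment in the SAP |
|---|---|---|
| Device event in a participant who wore the device but was never dosed | Yes (16.1, from consent) | Excluded from the safety analyses (SAP 4) |
| Device event before the first dose in a participant later dosed | Yes (16.1) | Participant is in the Safety set. SAP 6.6 gives an end to the window but no start and no treatment-emergent rule, so nothing in the text removes the event |
| Device injury after a switch | Yes (16.1, 16.2.4.2) | After the start of new treatment, so past the cut-off (SAP 6.6) |
| SAE of any cause after a switch | Yes (16.2.4.1, 16.2.4.2) | Past the same cut-off |

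The first, third and fourth rows conflict with the protocol's collection rule. The second does not.

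**2. Do the other provisions of SAP 6.6 close the gap?**

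- *Sponsor-agreement clause.* It is worded for toxicities beyond 28 days. A switch can close the window sooner, and events between the switch and day 28 are then not clearly covered. Later events enter only by sponsor agreement.
- *Listing of all adverse events.* A listing gives no denominator and no rate. The text does not say that it covers participants outside the Safety set.
- *Special attention to procedure-related events.* No set, window or table is attached to it.

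**3. Wear time outside the window for one patient who switches**

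Assume a switch at the end of 4-week cycle k, with wear continued to week 24 as Protocol 10 plans. Wear after the cut-off is 24 − 4k weeks:

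- k = 1: 20 weeks, 20/24 = 83%
- k = 3: 12 weeks, 12/24 = 50%
- k = 5: 4 weeks, 4/24 = 17%

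**4. How many patients might be in this position**

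The documents give no switch rate. Assume exponential progression times and a switch at progression, and use the Japanese subgroup medians in Protocol 7. With 24 weeks = 24 × 7 / 30.44 = 5.52 months, the proportion by week 24 is 1 − 0.5^(5.52/median):

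| Japanese subgroup | Median PFS (months) | Proportion by week 24 |
|---|---|---|
| Palbociclib + letrozole | 22.2 | 15.8% |
| Placebo + letrozole | 13.8 | 24.2% |
| Palbociclib + fulvestrant | 13.6 | 24.5% |
| Placebo + fulvestrant | 11.2 | 28.9% |

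The range is about 16% to 29%. These are patients with some wear outside the window, not lost events.

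**The case against.** The best defence is that little is likely to be lost. Protocol 16 classes the procedure as no more than minimal risk. Inclusion criterion 4 requires patients to be initiating therapy, so never-treated wearers should be rare. Medically important research-related injury goes to the sponsor at once under Protocol 16.2, whatever the tables show. SAP 6.6 flags procedure-related events and lists all adverse events. The study is descriptive, and no objective or endpoint is a device-event rate. All of this stands, and it keeps the point minor. It does not remove the conflict: SAP 4 and 6.6 state rules that leave out events the protocol says must be recorded.

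A reader might also infer more than the documents support:

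- **That all pre-treatment device events are lost.** This is established only for participants who were never treated.
- **That non-serious device events cannot be identified.** Protocol 16.2.5 says "if the investigator determines that an SAE is associated with study procedures, the investigator must record this causal relationship", and it names only SAEs for that entry. However, 16.1 requires every adverse event to be assessed for a relation to study participation, and says that events attributed to the procedure, serious or not, are in the database. The CRF is not among the documents, so a missing field cannot be asserted.
- **That the feasibility objective is affected.** SAP 6.2.6 defines feasibility by counts of data and time to wearable failure. Device events do not enter it.
- **That the reported rate is biased low.** Uncounted post-switch events would push it down. Excluding untreated wearers also shrinks the denominator, so that part could move the proportion either way.
- **That up to 63% of patients are affected.** That figure follows from the 3.8-month median of the overall PALOMA-3 placebo arm. The study is in Japanese patients, and the protocol gives Japanese medians.

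**Conclusion.** Wrong as written, minor severity. The SAP's safety set and cut-off conflict with the protocol's collection rule in two places. Device-related events in never-treated wearers are excluded by SAP 4. Device injuries and SAEs recorded after a switch fall past the cut-off in SAP 6.6 and are not assured a place in the summaries.

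The effect on results cannot be quantified, because the documents give no device-event rate, switch rate or untreated rate. The 16% to 29% illustration rests on exponential times, a switch at progression, Japanese subgroup medians applying to this cohort, and wear continuing to week 24. The wearable is the study's one qualifying procedure, but it should not be called the only risk of participation: Protocol 15.1 also names the processing of personal data.

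**What to change.** Change the SAP only:

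1. **SAP 4.** Add a device safety set of all enrolled participants who wore the device at least once, treated or not. The Evaluable set is close, since it admits untreated participants with at least one device metric, but it also admits participants with application data only.
2. **SAP 6.6.** Add one table of study procedure-related adverse events and research-related injuries in that set, from consent to 12 hours after completion of the procedure, regardless of treatment start or switch.
3. **SAP 6.6.** Reconcile the cut-off at the start of new treatment with Protocol 16.2.4.2, so that it is clear where SAEs recorded after a switch are summarised.

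Leave the drug-related safety tables otherwise unchanged. A change to Protocol 16.2.5 or the CRF is not proposed: planned data collection ended on 28 February 2023, before SAP version 1.1 of 4 April 2023, and the SAP change uses events that the protocol already collects. The cost is a few sentences and one extra table.
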